### **Blinding**

Due to the objectives of the study, the identity of test and control treatments will not be known to investigators, research staff, or patients. The following study procedures will be in place to ensure double-blind administration of study treatments.

Access to the randomization code will be strictly controlled.

A taste-matching agent.

Packaging and labeling of test and control treatments will be identical to maintain the blind.

Blinding of K+: All safety K+ values will be blinded. A protocol driven approach for management of K+ will be followed. These data will also be made available to the DSMB for review.

Blinded-end point assessment: Data sets will be de-identified and replaced with a random number. The newly generated data set will be saved and the data identity key will be stored in a secure location.

The study blind will be broken on completion of the clinical study and after the study database has been locked.

During the study, the blind may be broken only in emergencies when knowledge of the patient's treatment group is necessary for further patient management.

## **Formulation of Test and Control Products**

### **Formulation of Test Product**

Spironolactone is an antihypertensive potassium sparing diuretic and Mineralocorticoid (Aldosterone) Receptor Antagonist.

### **Formulation of Control Product**

A matching placebo will be provided.

### **Dosage**

During the dose escalation phase, Spironolactone dosing will start at 12.5 mg PO and escalate to 25 mg or maxim tolerated dose. The dose may need to be adjusted during the study due to safety lab results (e.g. K+) or if BP<100 mmHg.

### **Study Drug Accountability**

An accurate and current accounting of the dispensing and return of study drug for each subject will be maintained on an ongoing basis by a member of the study site staff. The number of study drug dispensed and returned by the subject will be recorded.

### **Measures of Treatment Compliance**

Subjects will be asked to keep a patient diary noting the day and date they take their study drug and any adverse events. They will be asked to bring their patient diary to each study visit along with all used and unused study drug containers.

## **HYPERKALEMIA MANAGEMENT**

One of the most significant complications of the study medications is hyperkalemia. This risk is of particular importance in this study population as diabetic patients with chronic kidney disease are at increased risk for selective aldosterone deficiency, predisposing them to the development of hyperkalemia. Mild to moderate hyperkalemia is generally not associated with significant cardiac toxicity, especially when it is chronic (e.g., in dialysis patients) or slowly developing. In contrast, severe ( $> 6.5$  mEq/L) or rapidly developing hyperkalemia is likely to be associated with the development of ECG abnormalities ranging from peaking of the T- wave; to atrial, AV nodal and ventricular conduction delays; and ultimately, with very severe hyperkalemia, to ventricular fibrillation.

Dietary intake of potassium is a major factor in producing hyperkalemia and transient dietary increases in potassium intake can precipitate hyperkalemia in our patients. For example, a single high potassium meal prior to blood draw could result in high potassium at the time of the draw but later on a repeat the potassium may be much lower, as much as 1 mEq/L lower.

Decreased cellular uptake of potassium occurs when insulin is relatively deficient. Even a patient who is not on insulin can have relative insulin deficiency (also known as insulin resistance). Generally decreased cellular uptake of potassium occurs when a patient has ingested a high potassium diet but does not have enough insulin to drive potassium into the cell. This can result in transient hyperkalemia.

Factors that impair renal excretion of potassium and can contribute to hyperkalemia in addition to the study medication include: 1) decreased GFR; 2) drugs including NSAIDS (e.g. ibuprofen), COX-2 inhibitors (e.g. celecoxib) and 3) any process which decreases distal tubular flow rate such as can occur in the setting of volume depletion.

One or all of the above factors can be operative in the same patient. For example, a volume depleted patient can have relative insulin deficiency, a high potassium intake and have taken NSAIDS for pain while ingesting the study medication.

Subjects will be counseled to avoid medications that may increase the risk of hyperkalemia, such as non-prescription non-steroidal anti- inflammatory medications, and potassium-containing salt substitutes. All subjects will be monitored for the development of hyperkalemia at each follow-up visit and an ECG will be obtained for any potassium value  $> 6.0$  mEq/L.

The aggressiveness of treatment of hyperkalemia will depend on the degree of elevation and the presence or absence of ECG findings.

#### **Treatment of hyperkalemia for Potassium $> 5.0$ meq/L: Dietary potassium**

If during follow-up, a subject's potassium level increases to  $> 5.0$  mEq/L, he/she will be prescribed a low potassium diet (0.7-0.8 meq/kg/day to a maximum daily intake of 60 meq/day). An initial step would be to restrict potassium in the diet. Input from a dietitian can be helpful.

There is potassium in most foods, but certain foods are especially high in potassium and should be avoided. Some high potassium foods can be eaten after leaching the potassium by soaking. Many salt substitutes are potassium chloride and should be avoided. Fruits and vegetables should be limited to four servings per day. Dairy products should be limited to 1 cup/day.

#### High Potassium Foods (avoid):

Fruits and juice: apricots, avocado, banana, cantaloupe, honeydew, dried fruit (dates, raisins, prunes, figs), citrus fruits (orange, grapefruit, nectarines)

Vegetables: artichoke, butter beans, dried peas or beans, potatoes (unless leached), sweet potatoes, Swiss chard, winter squash.

Other: chocolate, molasses, nuts, peanuts

#### Medium potassium foods: Limit to one serving (1/2 cup)/day:

Fruits: blackberries, cherries, peach (1), pear (1), raspberries, strawberries, watermelon (1 cup), plums (2)

Vegetables: broccoli (cooked), carrot, mushroom, peas, corn, cabbage, eggplant, spinach (cooked), pumpkin, tomato, potato (leached), beets

Low potassium foods (note that portion size is 1/2 cup, eating a large amount of a lower potassium food will make it a higher potassium food)

Fruits (including juice): Apple, blueberries, cranberries, grapes, tangerine (1 small) Vegetables: green beans, wax beans, cucumber, green pepper, lettuce, yellow squash

Leaching vegetables: For potatoes, sweet potatoes, carrots, beets and rutabagas:

Peel and slice vegetables 1/8 inch thick

Rinse

Soak for a minimum of two hours in warm water, using 10 times the amount of water to the amount of vegetables. If soaking longer, change the water every few hours

Rinse under warm water

Cook with five times the amount of water to the amount of vegetable

#### **Treatment of hyperkalemia for Potassium > 5.5 meq/L**

In addition to a low potassium diet, if the potassium level increases to >5.5 mEq/L, conservative measures should be instituted.

Possible approaches include:

Increase in diuretics if volume depletion is not a concern. Volume depletion could worsen hyperkalemia

Administration of chronic alkali supplements, such as sodium bicarbonate 1300mg bid if acidosis is present

Liberalization of salt intake (if volume status and uncontrolled blood pressure are not concerns)

Chronic use of low-dose sodium polystyrene sulfonate (15-30 grams 3x/week)

#### **Treatment of hyperkalemia for Potassium > 6.0 meq/L**

If the potassium level is > 6.0 mEq/L, the study medication will be held until the level decreases to < 5.5 mEq/L.

Acutely to treat the potassium:

An ECG should be checked. If there are no ECG changes and potassium level is < 6.5, then Kayexalate alone (60 grams) may be sufficient. If there are ECG changes, treatment would include insulin/glucose, beta-agonists and possibly calcium and bicarbonate. If there are ECG changes or if the potassium level is > 6.5 meq/L, the patient should be treated in the emergency room. If there are ECG changes, the patient should be placed on a cardiac monitor.

Reinstitution of Study Medication

If the potassium level was > 6.5, then the study medication will be permanently discontinued and the patient will be removed from the trial. If this is the second episode where potassium > 6.0, then the study medication will be permanently discontinued and the patient will be removed from the trial.

Recheck potassium level 7- 14 days after discontinuation. If K+ is > 5.5 mEq/L, do not restart study medications. Repeat potassium again in 7-14 days. If K+ is ≤ 5.5 mEq/L, the study medication will be reinstated at 50% of prior dose.

If the study medication was restarted, check potassium level again in two weeks, if K+ is:

- o > 6.0: stop study the study medication permanently
- o 5.5-6.0: treat K+, maintain current dose of the study medication
- o < 5.5: mEq/L and patient is on at least 12.5 mg spironolactone, increase spironolactone to 25mg daily.

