### **Side Effects Related to Study Drug**

#### ***Common Side Effects***

- Hyperkalemia: We anticipate that approximately 1% of patients may develop serious hyperkalemia that may warrant discontinuation. However this may be considerably higher in patients with GFR of 40-50 ml/minute who will constitute a minority of the patients in the trial.
- Increases in BUN and creatinine
- Gynecomastia or breast discomfort. Gynecomastia is a well-described adverse effect of spironolactone and is related to dose and duration of treatment; we anticipate that

approximately 10% of patients may develop gynecomastia that may warrant discontinuation. Generally, discontinuation of treatment results in resolution of gynecomastia.

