## CRITERIA FOR EVALUATION

### Co-Primary Efficacy Endpoints

The co-primary outcome measure is change in 24-hour SBP in Spironolactone treated patients versus placebo and percent change in total atheroma volume (PAV) in thoracic aorta of Spironolactone vs placebo.

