#### **Exclusion Criteria**

1. Uncontrolled hypertension (SBP>160 and/or DBP>95 mmHg at visit 0 (screening) Protocol Number: 09-16-32 Confidential Version #: 1.5 Revised 01 April 2020 Page 14 of 39 and SBP >145 mm Hg at visit 2).
2. GFR (MDRD) of <15 at visit 0 (screening)
3. Hyperkalemia defined as serum K+ $\geq$  5.1 meq/L at visit 0 (screening)
4. LDL cholesterol >150 mg/dL
5. Plasma triglycerides > 400 mg/dl
6. Contraindications to MRI (metallic implants, severe claustrophobia).
7. Acute coronary syndrome, Transient ischemic attack, CVA or critical limb ischemia during the last 6 months or coronary/peripheral revascularization within the last 3 months.
8. Evidence of a secondary form of hypertension
9. Initiation of new therapy with statins, ACEI/ARB, antioxidants, CCBs, diuretics,  $\beta$  blockers
10. Type I diabetes mellitus
11. Known contraindication, including history of allergy to Spironolactone
12. Any surgical or medical condition which might alter pharmacokinetics of drug (e.g. renal transplant, liver failure, liver transplant)
13. Concurrent potentially life threatening arrhythmia or symptomatic arrhythmia.
14. Significant hyponatremia defined as Na<130 meq/L
15. History of prior malignancy including leukemia and lymphoma (but not basal cell skin cancer, cured squamous cell cancer and cured prostate cancer).
16. History of any severe, life-threatening disease.
17. Any surgical or medical conditions which place the patient at higher risk derived from his/her participation into the study, or likely to prevent patient from complying with requirements
18. History of drug abuse within the last 2 years, noncompliance and unwillingness/inability to consent
19. Pregnant women and nursing mothers
20. Class III or IV Congestive Heart Failure
21. Primary Hyperaldosteronism

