## **DISCONTINUATION OF SUBJECTS**

### **Early Discontinuation of Study Drug**

A subject may be discontinued from study treatment at any time if the subject, the investigator, or the Sponsor feels that it is not in the subject's best interest to continue. The following is a list of possible reasons for study treatment discontinuation:

Subject withdrawal of consent (or assent)

Subject is not compliant with study procedures

Adverse event that in the opinion of the investigator would be in the best interest of the subject to discontinue study treatment

Protocol violation requiring discontinuation of study treatment

Lost to follow-up

Sponsor request for early termination of study

Positive pregnancy test (females)

If a subject is withdrawn from treatment due to an adverse event, the subject will be followed and treated by the Investigator until the abnormal parameter or symptom has resolved or stabilized.

All subjects who discontinue study treatment should come in for an early discontinuation visit as soon as possible and then should be encouraged to complete all remaining scheduled visits and procedures.

All subjects are free to withdraw from participation at any time, for any reason, specified or unspecified, and without prejudice.

Reasonable attempts will be made by the investigator to provide a reason for subject withdrawals. The reason for the subject's withdrawal from the study will be specified in the subject's source documents.

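### Patients permanently stopped for high potassium are to be removed from the trial under one section and kept in follow-up under another; the two instructions need reconciling

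*Combined protocol and SAP*

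**What the plan says.** Under Treatment of hyperkalemia for Potassium > 6.0 meq/L, the paragraph on reinstating study medication names two triggers: a potassium above 6.5, and a second episode above 6.0. For each it says "then the study medication will be permanently discontinued and the patient will be removed from the trial".

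Early Discontinuation of Study Drug gives a general rule: "All subjects who discontinue study treatment should come in for an early discontinuation visit as soon as possible", after which they "should be encouraged to complete all remaining scheduled visits and procedures". That rule has no exception for hyperkalemia. Neither section mentions the other, and nothing says which takes precedence.

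The outcomes concerned are set out under Co-Primary Efficacy Endpoints: "The co-primary outcome measure is change in 24-hour SBP in Spironolactone treated patients versus placebo and percent change in total atheroma volume". In the Main Study Phase schedule (Table 4), MRI appears at baseline and at the final visit only. Clinical Assessments places 24-hour blood pressure at Visits 2 and 6.

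On frequency, Common Side Effects says: "We anticipate that approximately 1% of patients may develop serious hyperkalemia that may warrant discontinuation". It adds: "However this may be considerably higher in patients with GFR of 40-50 ml/minute who will constitute a minority of the patients in the trial".

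**The concern.** The hyperkalemia wording ends trial participation, while the general wording asks the same patient to stay. With several sites taking part, the same event could be handled differently from one site to the next.

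What is at stake is mainly the atheroma endpoint. It needs the final MRI, and a removed patient has no scheduled follow-up scan. An early discontinuation visit might supply one, but the protocol lists no procedures for that visit, so an exit MRI is neither required nor ruled out.

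The reason for removal is related to treatment. Hyperkalemia Management counts high potassium among the most important complications of the study medication, so removals would probably be more frequent on spironolactone. They would not be confined to it: the rule applies to both arms, and the same section lists diet, reduced GFR, other drugs and volume depletion as causes. The statistical section, as written, has no missing-data rule for such patients, and the later SAP that it promises could not recover a scan that was never taken.

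**Working it through.** **The two texts side by side**

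| Question | Hyperkalemia section | Early discontinuation section |
|---|---|---|
| Who | Potassium above 6.5, or second episode above 6.0 | All who stop study treatment |
| Study drug | Stopped permanently | Already stopped |
| Trial follow-up | Removed | Early discontinuation visit, then encouraged to complete the rest |

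The first two rows agree; the third does not. Reading removal from the trial as merely coming off drug does not help, because the same sentence already states separately that the drug is stopped.

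**The plan's own sample size**

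Inputs from Aim 1: CV 0.83, 1.5-fold difference, two-sided alpha 0.05, 80% power, 20% loss.

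- SD on the log scale = sqrt(ln(1 + 0.83²)) = 0.724.
- Target effect = ln(1.5)/0.724 = 0.405/0.724 = 0.560 SD.
- Two-sample t-test: 51.02 per group, rounded up to 52, as stated.
- Recruitment: 104/0.80 = 130, or 65 per arm, as stated. The loss allowance is 0.20 × 65 = 13 per arm.

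**How many removals**

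The only documented rate is the 1% from Common Side Effects, used here as a proxy for removal.

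- Expected on spironolactone: 65 × 0.01 = 0.65.
- Chance of at least one: 1 − 0.99^65 = 0.48.
- Chance of two or more: 0.14.

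**How much bias**

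If a fraction p of an arm is removed and those patients differ from the rest of the arm by s SD in atheroma change, the mean of the remaining patients is off by p × s. Between arms, the bias is the difference in removal rates times s. Two assumptions not in the documents: s between 0.5 and 1 SD, and no removals on placebo.

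| Excess removal rate on spironolactone | Bias (SD) | Share of 0.560 SD target | Two-sided type I error, 52 per arm |
|---|---|---|---|
| 1% (documented proxy) | 0.005-0.010 | 0.9-1.8% | 0.0501-0.0503 |
| 1 of 65 = 1.5% | 0.0077-0.0154 | 1.4-2.7% | 0.0502-0.0507 |

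For the bias to reach 10% of target (0.056 SD), the excess would have to be 0.056/1 = 5.6% (3.6 of 65) or 0.056/0.5 = 11.2% (7.3 of 65). That is about 6 to 11 times the documented rate. Type I error there would be about 0.059.

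**Power**

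If one patient is lost from one arm beyond the 20% allowance, power goes from 0.808 to 0.804; with two lost it is 0.800.

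**The case against.** The strongest reply is that a specific rule overrides a general one. The hyperkalemia rule is mandatory and tied to a named event, while the early discontinuation section opens with discretionary stopping and only encourages later visits. Its reference to all subjects cannot be fully literal either, since its reasons for stopping include loss to follow-up and withdrawal of consent. This reading is possible, but the protocol states no such precedence, so a site would have to guess. The conflict stands.

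The second reply is that the numbers are trivial: fewer than one expected removal, well inside the loss allowance, with a bias that depends on an assumed shift. That is right, and it limits how much weight the point carries.

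The third concerns the 1%. It refers to serious hyperkalemia that may warrant stopping, whereas removal requires a potassium above 6.5 or a second episode above 6.0, possibly a narrower group. So 1% may be too high. It may also be too low, since the protocol expects more at GFR 40-50 and the renal exclusion is only "GFR (MDRD) of <15 at visit 0 (screening". The documents do not settle the direction.

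A reader might also infer more than the text supports:

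- That the instruction for potassium above 6.0 after a restart, "stop study the study medication permanently", leaves trial status open. It does not. Restart follows a hold for potassium above 6.0 and requires a value of 5.5 or less, so a later value above 6.0 is already a second episode, whose trial status is stated.
- That both co-primary outcomes are generally lost. The 24-hour blood pressure is complete by Visit 6, and a second-episode removal needs a hold, a 7-14 day recheck, a restart and a two-week check, which leaves little time before that visit.

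**Conclusion.** The two follow-up instructions are incompatible and should be reconciled. As written, the hyperkalemia wording gives up the only follow-up MRI for a reason related to the drug.

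The expected effect is small: about 0.65 removals among 65 spironolactone patients, and a bias of about 1-2% of the target effect. This rests on the 1% proxy, an assumed 0.5-1 SD shift and no placebo removals. The direction of any bias is unknown.

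It would be tempting to conclude that the primary result is in danger. The documents do not support that: a bias of even 10% of target needs an excess removal rate for which they give no figure. The case for change is that it removes a plain contradiction and keeps data already scheduled, at little cost.

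**What to change.** Reconcile the two removal sentences in the hyperkalemia section with Early Discontinuation of Study Drug by treating permanent discontinuation of study drug and withdrawal from trial follow-up as separate events. Unless the sponsor states a reason for an exception, the existing general provision should apply to these patients: early discontinuation visit, then the remaining scheduled visits including the final MRI, subject to consent. Their data should be analysed in the randomised arm.

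If the sponsor does intend an exception, the early discontinuation section should say so and list what is measured at the early discontinuation visit.

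The change concerns follow-up only; it neither alters nor proposes any potassium threshold, dose or stopping rule. The cost is a short amendment and a few off-drug visits and MRIs already on the schedule; at 1%, that is fewer than one expected spironolactone patient. The documents give no cost figures. Some data will still be missing, because continued follow-up is only encouraged.

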### Main Study Phase

TABLE 4	SCREEN		RUN-IN PHASE		RANDOMIZATION PHASE										
					DOSE ESCALATE				TREATMENT PHASE						
	MONTH*	M1	M1	M2	M2	M 2	M 3	M 5	M 7	M 9	M 11	M 12	M 13		
WEEK	W 1	W2	W3	W4	W5	W6	W8	W9	W11	W17	W25	W33	W41	W45	W53
VISIT NUMBER	0		1	2	3	4	5	6	TF1	7	TF2	TF3	TF4	8	
Screening Labs (BMP, Lipid panel, HbA1C, Urine sample Alb/Creat)	X														
Safety Lab (BMP)				X	X	X	Opti onal	X		X					X
History/ Targeted assessment		X								X					X
EKG		X													
Vital Signs or 24-hour BP cuff *( includes central aortic BP)	X	X	X*		X		X*		X						X
Phone Call								X		X	X	X			
MRI				X											X
Research Labs/Monocyte Studies, including PIP, PIIINP, CITP and chemokines CCL2, CX3, CL1, and CCL5				X			X								X
Insulin/Glucose (HOMA-IR)				X											X
HbA1C				X						X					X
Plasma Renin/Aldosterone				X											X
Medication Log		X			X		X	X	X	X	X	X	X		X
Pill counts			X				X		X						X
Dietary survey/instructions		X													X
Urine sample (Albumin/Creat)	X	X	X				X		X						X
Urine Na/K/Creat			X												
Interim Event log			X		X		X	X	X	X	X	X	X		X
Questionnaire & Instructions		X													

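### After a first potassium above 6.0 on 25 mg, the plan allows a return to 25 mg but requires no potassium check after that increase

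*Combined protocol and SAP*

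**What the plan says.** The rules are in the protocol's Hyperkalemia Management section, under the heading for potassium above 6.0 mEq/L.

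- Above 6.0, study drug is held. Above 6.5, it is stopped for good.
- A second event also ends treatment: "If this is the second episode where potassium > 6.0, then the study medication will be permanently discontinued".
- Potassium is rechecked 7 to 14 days after stopping, and again after a further 7 to 14 days if still above 5.5.
- At 5.5 or below, "the study medication will be reinstated at 50% of prior dose".
- After a restart, the instruction is to "check potassium level again in two weeks". Above 6.0 the drug stops permanently. At 5.5 to 6.0 potassium is treated and the dose kept. Below 5.5, if the "patient is on at least 12.5 mg spironolactone, increase spironolactone to 25mg daily".

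That is the last instruction in the section. Earlier, the same section says: "All subjects will be monitored for the development of hyperkalemia at each follow-up visit". The Main Study Phase text under Study Design attaches potassium and creatinine checks to the first escalation to 25 mg. Table 4 (Schedule of Events, Main Study Phase) sets the scheduled BMPs.

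**The concern.** A patient who was on 25 mg goes back to the dose on which potassium exceeded 6.0. The value below 5.5 that permits this was obtained on 12.5 mg, so it does not show that 25 mg is now tolerated. The first escalation to 25 mg, in patients with no such event, does have laboratory checks around it. The re-escalation, in patients who have had one, has none after the step.

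This is a patient-safety point. Every participant is on an ACE inhibitor and/or ARB (inclusion criterion 4), GFR down to 15 is admitted (exclusion criterion 2), and the protocol itself describes diabetic patients with kidney disease as prone to hyperkalemia. The permanent-stop rule for a second value above 6.0 can act only if potassium is measured. The Blinding section makes safety potassium values blinded and their management protocol-driven, so a step the protocol leaves out is less likely to be supplied by site judgment.

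**Working it through.** The plan gives no figure for this interval, so there is none to reproduce. The check is calendar arithmetic on Table 4.

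**1. Who reaches the rule.** First event above 6.0 and not above 6.5; prior dose 25 mg, restarted at 50% × 25 = 12.5 mg; potassium below 5.5 two weeks later. A patient previously on 12.5 mg restarts at 6.25 mg and does not meet the 12.5 mg condition.

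**2. Scheduled BMPs, read by column.** W4, W5, W6, W8 (optional), W9, W17, W53. The row is blank at W25, W33, W41 and W45.

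**3. Are the contacts in between blood-draw visits?** W25, W33 and W41 are labelled TF2 to TF4. By column, they carry marks only for phone call, medication log and "Interim Event log"; W45 carries none. Some rows look displaced. Phone-call marks sit at W9, W17, W25 and W33, while TF1 to TF4 sit at W11, W25, W33 and W41; moved one column right, the marks match the TF labels exactly. The 24-hour BP marks (W3 and W8) are likewise one column away from the visits 2 and 6 named under Clinical Assessments (W4 and W9). Reading TF as telephone follow-up is therefore an inference, though a well-supported one. The BMP row as a whole cannot move right, because its exit mark is already in the last column. Moving it left only brings the last draw before exit earlier.

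**4. Week of return to 25 mg.** Event week + hold + 2 weeks at half dose. The hold is 1 to 2 weeks with no repeat recheck, or 2 to 4 weeks with one repeat.

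- Event at W17: 17 + 1 + 2 = W20, to 17 + 4 + 2 = W23.
- Event at W9: 9 + 1 + 2 = W12, to 9 + 4 + 2 = W15.

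**5. Exit week.** Table 4 places the exit MRI and BMP at W53 but the visit 8 label at W45. Method of Assigning Subjects to Treatment Groups gives 4 weeks of escalation followed by 48 weeks of treatment. From randomization in the W4 column, that is 4 + 4 + 48 = W56. So W53 (53 − 4 = 49 weeks after randomization) is nearer the text than W45 (45 − 4 = 41 weeks), but neither matches 52 weeks. The 54 weeks under Aim 1 equals 2 + 4 + 48, which counts from the start of run-in.

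**6. Time from the increase to the next scheduled BMP.**

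| Event found at | Increase | Next scheduled BMP | Weeks after increase |
|---|---|---|---|
| W9 | W12–W15 | W17 | 17 − 15 = 2 to 17 − 12 = 5 |
| W17 | W20–W23 | exit W53 | 53 − 23 = 30 to 53 − 20 = 33 |
| W17 | W20–W23 | exit W45 | 45 − 23 = 22 to 45 − 20 = 25 |
| W17 | W20–W23 | exit about W56 | 56 − 23 = 33 to 56 − 20 = 36 |

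**7. The interval everyone has.** From W17 to exit without a BMP: 53 − 17 = 36, 45 − 17 = 28, or 56 − 17 = 39 weeks.

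**The case against.** The best reply is the sentence promising hyperkalemia monitoring at each follow-up visit. It sets no timing after a dose increase, however, and Table 4 puts no laboratory test at the contacts between visit 7 and exit. At most, the text and the table disagree.

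Other safeguards exist. The Dosage section allows adjustment for safety labs, and diet and conservative measures apply above 5.0 and 5.5. A potassium of 6.0 or more is an urgent alert, a value above 6.0 is an adverse event, and the DSMB reviews data every three months. These keep an affected patient in view, but each acts on a result already obtained; none orders a draw. An unscheduled test is permitted but not required.

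A reader might infer more than the documents support:

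- *That the increase is made without any potassium check.* It is not: it depends on a value below 5.5, two weeks after a half-dose restart.
- *That potassium is never measured again.* The exit BMP is scheduled for everyone, and an event found at W9 is followed by the W17 draw.
- *That the re-challenge rule creates the gap of many months.* The sparse schedule after W17 applies to all participants.
- *That re-challenge is itself wrong.* The protocol explains that one high-potassium meal can raise a reading by as much as 1 mEq/L, which is a fair reason to try again.

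It also stands that the group is narrow. No scheduled BMP falls between W17 and exit, so any later event would have to be found by an unscheduled test.

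**Conclusion.** The point holds in limited form: after re-escalation to 25 mg following a first potassium above 6.0, the plan requires no potassium check, and for events found at W17 or later Table 4 does not supply one before exit. For a W17 event, the wait after the increase is 30 to 33 weeks on the column reading of Table 4, with 22 to 25 and about 33 to 36 weeks on the other two readings of the exit week. For a W9 event it is 2 to 5 weeks, and the schedule largely covers it.

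The missing draw is the defect; the length of the wait mainly reflects the trial-wide schedule. The number of patients affected is small and cannot be estimated from the documents. The change is worth making because it is cheap and because the second-event stop rule depends on it.

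Assumptions: Table 4 columns are read by position despite some displaced rows; TF contacts involve no blood draw; there is at most one repeat recheck before restart; the visit window of ±7 days is ignored.

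**What to change.** In Hyperkalemia Management, after the line for potassium below 5.5, add:

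> *Obtain a BMP about two weeks after any increase to 25 mg that follows hyperkalemia, even if the next scheduled contact is by telephone. Above 6.0: stop study medication permanently. 5.5–6.0: treat and keep the dose. Below 5.5: continue 25 mg.*

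The cost is one sentence and one extra draw, possibly with an extra visit, for a few patients. For a W17 event, the first potassium after the increase would come at about 2 weeks rather than at exit. The W17-to-exit interval for other participants is unchanged. While editing, the sponsor could also reconcile Table 4 with the statement about monitoring at each follow-up visit and with the stated exit week.
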